Patients will be recruited for the program after obtaining a preliminary diagnosis of ASD from the developmental paediatrician. ADOS-2 will be administered to confirm the diagnosis and thus participation in the research study. We will not be advertising this study to the public.

Pilot

An initial pilot feasibility study with 6 children and families will be conducted at the start of the project to identify any practical issues or weaknesses in the program or protocol before full scale evaluation.

Sample Size Calculation

The randomized trial is designed as a non-inferiority study to compare the changes in MSEL between 2 interventions. We expect that the change in MSEL score for the subjects in the new intervention arm will be slightly better than that in the control arm by 1.5 units. Assuming the SD of changes in MSEL score is 15 units, with 5 units as the non-inferiority margin, based on a one-sided test with 80% power and 5% significance level, it is sufficient to recruit 132 subjects (66 in each arm). We decided to recruit 200 subjects in total (100 in each arm) after considering withdrawals and lost to follow up. The computation was performed using a proprietary software programmed in R.

Randomisation Process and Blinding

Computer-generated randomisation will be used to randomly assign the participants to one of the intervention groups. Block randomisation will be used to allocate the recruited subjects into one of the interventions. A randomisation list will be generated by the study statistician and envelopes will be prepared. Although the allocation of intervention will be concealed and the study team will not know in advance which subject will receive which intervention, the blinding will not be possible once the intervention is assigned. Assessors of the initial and final MSEL were not told of the intervention status of the patient to avoid bias in outcome assessment. Blinding of the parents is not possible in the context of this study. Phone calls will be made if necessary to confirm appointments and/or before commencing consultation over video conference in the Telerehab group. Parents in both study arms will be encouraged to spend 2h per week in quality interactions with their children.

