The comparator for this study will be the standard model of delivery for EI which are clinic-based (face-to-face) sessions with the patients and their primary caregiver. The **variable treatment component** between telerehab and the standard model of delivery is the number of video-conferencing vs clinic-based intervention sessions. The assumption is that all non-therapy related costs such as paediatrician reviews will be the same for subjects in both study arms.

Table 1: Variable components of care between standard and telerehab care model

	Standard Model	Telerehab Model
Clinic-based intervention (45mins + 15mins)	16 sessions	2 sessions
Video-conferencing (30mins + 15mins)	0 sessions	16 sessions
Total Therapy time	720mins + 240 mins (admin)	570mins + 270 mins (admin)

Analysis Approach

We will take on two approaches to calculate the ICER. First, is the use of patient-level data for cost-effectiveness analysis. Second, we will use estimates generated from analyses Monte Carlo simulation to estimate the cost-effectiveness through parameters (mean, standard errors) obtained from the study. This will be decided by the analyst with the justification for the approach documented.

Time Horizon

The time horizon considered will be the duration of the program (around 1 year), from enrolment till final review. The cost and outcomes data collected will be limited to the duration of the program. It will be hard to justify extrapolations and assumptions after the program after the patient has transited out of NUH CDU to EIPIC, where treatment frequency and intensity will be substantially variable.

Univariate sensitivity analysis

One-way sensitivity analysis will be performed to assess the impact of a change in parameters.

Probabilistic sensitivity analysis²

Probabilistic sensitivity analysis (PSA) will be performed by incorporating the degree of uncertainty for each parameter. This involves assigning a primary mean value for each model parameter (mean cost, number of visits, probabilities) and the distribution of possible values. Monte Carlo simulation was used to estimate mean expected costs and outcomes, and statistical measures of expected variance (SD) around the mean for 1,000 iterations drawn from the distributions defined.

Direct Healthcare Costs

Health sector cost

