We will examine the primary outcome, Mullen's Scale of Early Learning (MSEL) Early Learning Composite Score (ELC) as the key outcome of interest (i.e. the denominator for ICER). We will also examine the outcomes in VABS and JERI as outcomes of interest. Parameters for modelling for outcomes will be obtained from analyses specified in the previous section.

Input Data for Outcomes and Cost Data for the Model

The input data for the model from the survey administered is listed below in Table 2.

Table 2: Data Source and Parameters Estimates and Distribution for Cost-effectiveness Analysis

	Standard	Telerehab	Parameters Estimated	Distribution
Outcomes	Estimates from analysis from t-test/regression for: MSEL-ELC, VABS composite score and/or JERI	Estimates from analysis from t-test/regression for: MSEL-ELC, VABS composite score and/or JERI	Mean (SD) improvement in outcomes examined	Normal
Direct Healthcare Cost				
Attendance for therapy sessions	Number of clinic-based therapy sessions attended	Number of clinic-based and telerehab therapy sessions attended Telerehab consists of clinic-based sessions at the start of the program + telerehab sessions	Mean (SD) of therapy session attended across each study arm	Normal or gamma
Healthcare cost	Total cost of clinic-based therapy sessions	Total cost of clinic-based + telerehab therapy sessions	Number of visits * fixed cost per visit (standardized for FY2021/22)	Fixed
Direct Non-healthcare Cost				
Transport costs	Survey questions 
 • What mode of transport did you use to get here today? • How much did it cost? • Do you usually use this mode of transport to get to the clinic/CDU? • If no, what is your usual mode of transport? • How much did it cost? 	Survey question 
 • What mode of transport did you use to get here today? • How much did it cost? • Do you usually use this mode of transport to get to the clinic/CDU? • If no, what is your usual mode of transport? • How much did it cost? 	The total transportation cost incurred by participants will differ between study arms by nature of the mode of delivery. The actual transportation cost will account for two-way (round trip) and the observed visits (accounting for missed appointments for example)	Normal

			Transport Cost = Total no. of trips * Mean transport cost * 2	

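### Table 2 lists Mean (SD) for two simulation inputs, outcomes and attendance, where the Analysis Approach specifies standard errors; the two conflict, and only the standard error is right for drawing an arm mean

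*Combined protocol and SAP*

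**What the plan says.** The Analysis Approach, under Cost-Effectiveness Analysis, offers two routes to the ICER: patient-level data, or a Monte Carlo simulation that will "estimate the cost-effectiveness through parameters (mean, standard errors) obtained from the study". The probabilistic sensitivity analysis (PSA) subsection then assigns each model parameter a mean and a distribution, and reports "statistical measures of expected variance (SD) around the mean for 1,000 iterations drawn from the distributions defined".

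Table 2 sets out those parameters and distributions. Two of its rows name a measure of spread:

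- **Outcomes.** The source in both arms is "Estimates from analysis from t-test/regression for: MSEL-ELC, VABS composite score and/or JERI". The parameter is "Mean (SD) improvement in outcomes examined", distribution Normal.
- **Attendance.** The parameter is "Mean (SD) of therapy session attended across each study arm", distribution Normal or gamma.

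The other rows name none. Healthcare cost per visit is fixed, transport cost is Normal, additional care uses a Beta probability and a Gamma cost, and the productivity rows give no distribution.

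The planning values are in the Sample Size Calculation: "Assuming the SD of changes in MSEL score is 15 units", telerehab "slightly better than that in the control arm by 1.5 units", and "with 5 units as the non-inferiority margin". That section requires 66 per arm and sets recruitment at 100 per arm.

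**The concern.** The ICER is built from differences between arm means. A PSA has to express how uncertain those means are, and the spread of a mean's sampling distribution is its standard error. The SD between children measures how much children differ from one another and does not shrink as the trial grows. Drawing an arm mean with that SD simulates single children and reports their variation as if it were uncertainty about the programme.

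The Analysis Approach names the right quantity and Table 2 names another. The plan's other uses of SD as a data summary make the between-child reading of Table 2 a natural one: the Sample Size Calculation uses SD for the spread of changes in MSEL score, and the Quantitative Outcomes section uses mean and SD as its descriptive summary. The PSA draws from the distributions defined for it, and Table 2 is where they are listed. An analyst who follows the table literally would report far too much uncertainty about the effect. Attendance matters as well: the cost per visit is fixed, so an over-wide attendance draw passes straight into the health-sector cost component.

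**Working it through.** **Inputs.** From the Sample Size Calculation: SD of change 15, expected difference 1.5, margin 5, one-sided 5% level, 80% power, 66 per arm needed, 100 per arm recruited. The MSEL score behind the SD of 15 is not named there; I apply the figure to the MSEL outcome in the model. The inflation ratio in step 2 does not depend on it.

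**1. The plan's own figure.** n per arm = 2 × (1.6449 + 0.8416)² × 15² / (5 + 1.5)² = 2 × 6.183 × 225 / 42.25 = 65.9, which rounds up to 66, or 132 in total. This matches the plan; power at 66 per arm is 80.1%.

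**2. Inflation if an SD is drawn in place of an SE.**

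- One arm mean: SD / SE = 15 / (15/√n) = √n.
- Difference between arms: 15√2 / (15√(2/n)) = √n.

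The ratio is the same in both cases and the SD cancels, so it holds for attendance too, for which the documents give no SD.

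**3. Results for the MSEL difference, true difference 1.5.** The half-width is 1.96 × spread, and P(better effect) = Φ(1.5 / spread).

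| Input drawn | n per arm | Spread of difference | 95% half-width | P(better effect) | Inflation √n |
|---|---|---|---|---|---|
| SE | 66 | 15√(2/66) = 2.61 | 5.1 | Φ(0.574) = 72% | – |
| SE | 100 | 15√(2/100) = 2.12 | 4.2 | Φ(0.707) = 76% | – |
| SD | 66 | 15√2 = 21.2 | 41.6 | Φ(0.071) = 53% | 8.1 |
| SD | 100 | 15√2 = 21.2 | 41.6 | Φ(0.071) = 53% | 10.0 |

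At an assumed 50 analysed per arm the inflation would be √50 = 7.1.

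**4. Check by simulation, 1,000 draws as in the plan.** At 66 per arm the spread of the simulated difference was 20.9 with SD inputs and 2.66 with SE inputs, a 7.8-fold ratio. At 100 per arm it was 21.1 against 2.08, or 10.1-fold. Both agree with the formula within simulation error.

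**The case against.** The strongest reply is that the plan already has it right. The Analysis Approach specifies standard errors for this very simulation. Table 2 does not define its SD or call it patient-level, and it takes its outcome parameters from a t-test or regression, which normally supply a standard error. The PSA subsection also uses SD for the spread of simulated results, so the SD in Table 2 could be shorthand for the SD of the sampling distribution, which is the SE. Finally, Table 2 is titled for the whole cost-effectiveness analysis, including the patient-level route, where Mean (SD) is an ordinary summary.

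Much of this stands. A reader might infer that the plan has settled on patient-level SDs for its simulation. The documents do not support that: they conflict, and the between-child reading is an inference from usage elsewhere. The conflict itself remains, because nothing in Table 2 tells the analyst to depart from the usual meaning of SD.

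Two further inferences are tempting and fail:

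- **That the probability of cost-effectiveness would fall to about 50% whatever the trial found.** The 53% is the probability of a better effect at one assumed difference. With SDs drawn, a difference of 15 would still give Φ(15/21.2) = 76%. The plan also rests its judgement on whether telerehab saves cost. As an illustration, Table 1 plans 16 clinic sessions against 2. Assuming full average attendance and a child-level SD of 3 sessions per arm (my assumption), drawing SDs gives Φ(14/(3√2)) = Φ(3.30), above 99.9%, that telerehab uses fewer clinic sessions. At an assumed SD of 4 it is Φ(14/(4√2)) = Φ(2.47), about 99.3%.
- **That all PSA inputs, and so the ICER, are inflated 8-fold.** Only the outcomes and attendance rows carry an SD label.

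**Conclusion.** The point holds as a conflict between Table 2 and the Analysis Approach on what is drawn in the simulation. The standard error is the correct input. The size is conditional: if the between-child SD were drawn, the spread of the outcome and attendance parameters would be too wide by √n, about 8-fold at 66 per arm and 10-fold at 100. For the MSEL difference, the planning values would show a result pulled toward 50% and an interval of little use. These figures rest on the planned SD and difference and on equal arms; the ratio itself rests only on the number analysed per arm.

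How far total cost or ICER uncertainty would be affected cannot be worked out, because the documents give no spread for attendance and name no dispersion measure for transport and care costs. The primary non-inferiority analysis and the patient-level route to the ICER are untouched. The correction is worth making before analysis, since the PSA is stated as something that will be done.

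**What to change.** In Table 2, change Mean (SD) to Mean (SE) in the outcomes row and the attendance row, in line with the Analysis Approach. Add one sentence to the PSA subsection stating that each mean parameter in the simulation is drawn with its standard error; if a gamma is chosen for attendance, match it to the mean and its SE. The transport and care cost rows contain no SD label to replace: the added sentence covers their means, and the Beta probability of engaging additional care needs no relabelling.

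The cost is a wording change. It needs no new data, and the SE follows directly from an SD and the number per arm or from the t-test or regression output already planned.

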Health sector cost will be primarily attributed to the cost of treatment delivered by the institution, NUH CDU. The gross charges for paediatrician review, IIP review and administering surveys and assessments for the children are consistent in both study arms. Only variable cost between both study arms will be included. The variable cost includes the clinic-based intervention charges and video-conferencing-based intervention charges across both arms. The assumption for health sector cost will be that participants from both arms attend all the review and assessment sessions as they are essential to the intervention plan. The only variability would be attributed to defaulted therapy sessions.

Direct Non-Healthcare Costs

Transportation Costs

Transportation cost will be estimated using the responses from the baseline cost survey administered to caregivers. The total transport cost per study arm (standard vs telerehab) will be calculated by multiplying the *observed number of clinic-based visits* (accounting for missed appointments/therapy sessions) with the average cost of transportation indicated by the caregiver multiplied by two to account for round-trip travelling.

Caregiver and other care costs

Costs from other sectors include care cost from attending courses, hiring domestic helpers and/or other forms of care support for the child. This information is obtained from the cost survey administered to the parents.

Indirect Costs

Productivity Loss

Productivity loss will be calculated using the human capital approach. The human-capital method takes the patient's perspective (in this case the parent's time) and counts any hour not worked as an hour lost.

² <https://yhec.co.uk/glossary/probabilistic-stochastic-sensitivity-analysis/>
TRAutism HSDP Protocol_Version 8_19/08/2022

Productivity loss in this study will be primarily attributed to the caregiver taking time off from work to attend treatment with the patient (their child) and applying intervention strategies with the child. The time spent by caregivers includes the following:

- i. time spent on travelling CDU for treatment (two-way trip);
- ii. time spent on therapy sessions (30mins for video-conference, 45mins for clinic-based);
- iii. employment charges

Outcomes

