Follow-up time spent on intervention for caregivers	
 • In the past month, on average how much time (in hours) do you spend engaging (Speaking to, playing with, communicating with, doing activities) with your child per day? • In the past month, on average how much time (in hours) do you spend applying strategies learnt through the intervention with your child per day? 	
 • In the past month, on average how much time (in hours) do you spend engaging (Speaking to, playing with, communicating with, doing activities) with your child per day? • In the past month, on average how much time (in hours) do you spend applying strategies learnt through the intervention with your child per day? 	
Productivity loss in the time spend on delivering intervention to child
 
Time (in hour) spent on engagement with child + apply strategies learnt with child * hourly income of parent surveyed
	

Transport	
 • [baseline] How long did it take you to get to the clinic/CDU today? • Does it normally take you this long? • If no, how long do you usually take? 	
 • [baseline] How long did it take you to get to the clinic/CDU today? • Does it normally take you this long? • If no, how long do you usually take? • [At review] How long does it take for you to set up the computer before each telerehab session? 	Productivity loss in travelling time Time (in hour) required to travel to CDU today * 2 (two-way trip) * hourly income of parent surveyed	
------------------	-------------------------------------------------------------------------------------------------------------------------------------------------------------------------------------------------------------------------	------------------------------------------------------------------------------------------------------------------------------------------------------------------------------------------------------------------------------------------------------------------------------------------------------------------------------------	--------------------------------------------------------------------------------------------------------------------------------------------------	--

Data Cleaning Methodology and Approach

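### Table 2 collects telerehab set-up time but no caregiver-time formula uses it: a modest omission in telerehab's favour, to be fixed together with the missing visit count for travel time

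*Combined protocol and SAP*

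**What the plan says.** All places are in the combined protocol and SAP.

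- **Table 2, Indirect Cost from Productivity Loss, Transport row.** Both arms are asked about travel time to the clinic. The telerehab column alone adds, at review, "How long does it take for you to set up the computer before each telerehab session". The parameter for the row is labelled "Productivity loss in travelling time" and its only formula is "Time (in hour) required to travel to CDU today * 2 (two-way trip) * hourly income of parent surveyed".
- **Table 2, row on follow-up time spent by caregivers.** The other time formula is "Time (in hour) spent on engagement with child + apply strategies learnt with child * hourly income of parent surveyed".
- **Indirect Costs, Productivity Loss.** The human capital approach is adopted, which "counts any hour not worked as an hour lost". The itemised caregiver time is two-way travel, "time spent on therapy sessions (30mins for video-conference, 45mins for clinic-based", and employment charges.
- **Cost-Effectiveness Analysis, opening paragraph.** Because the trial is a non-inferiority trial, the economic conclusion rests on whether telerehab saves cost relative to standard care. Study Perspective names the societal view.
- **Table 2, Transport costs row** (direct non-healthcare cost). Transport cost is multiplied by the total number of trips, unlike travel time.

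**The concern.** Set-up time is a listed model input, yet no formula and no item in the caregiver-time list tells the analyst to value it. Under the plan's own costing principle it belongs in the total. Intervention: Telerehab Program describes the work: parents point the webcam at the activity area, use a headset, and have a portable microphone placed near the routine.

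The clinic counterpart appears to be counted already. The same section gives clinic sessions an extra 15 min for child and parents to settle in and leave. Table 1 separates 15 min of administrative time in both arms, and Productivity Loss then charges 45 min for a clinic session against 30 min for a video session. Getting ready thus seems to be charged for clinic sessions and not for video sessions.

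Leaving set-up out can only lower the telerehab cost, in an analysis whose conclusion is whether telerehab is cheaper.

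**Working it through.** **Inputs from the documents.** Standard arm: 16 clinic sessions. Telerehab arm: 2 clinic and 16 video sessions (Table 1; Annex 1 agrees, with 6 + 4 + 6 = 16 clinic sessions in the standard arm and 4 + 4 + 2 + 6 = 16 video sessions in telerehab). Counted time is 45 min per clinic session and 30 min per video session.

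**Assumptions, since the documents give neither figure.** Set-up of s = 5 to 15 min per video session; one-way travel of t = 30 to 60 min, with 15 min as an extra low case.

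**Step 1: reproduce Table 1.**
- Standard: 16 × 45 = 720 min, plus 16 × 15 = 240 min admin.
- Telerehab: 2 × 45 + 16 × 30 = 570 min, plus 18 × 15 = 270 min admin.

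All four figures match. The counted session-time difference is 720 − 570 = 150 min in telerehab's favour.

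**Step 2: time left out.** Omitted set-up is 16 × s.

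| s (min) | Omitted (min per family) | Session-time difference after adding it (min) |
|---|---|---|
| 5 | 80 | 150 − 80 = 70 |
| 10 | 160 | 150 − 160 = −10 |
| 15 | 240 | 150 − 240 = −90 |

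The session-time difference vanishes at 150 / 16 = 9.4 min.

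**Step 3: set it against the whole time saving.** With travel counted per session visit, telerehab avoids 16 − 2 = 14 round trips, or 28t min. The combined saving is 150 + 28t.

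| t (min) | Combined saving (min) | Share removed at s = 5 / 10 / 15 | Break-even s (min) |
|---|---|---|---|
| 15 | 570 | 14.0% / 28.1% / 42.1% | 35.6 |
| 30 | 990 | 8.1% / 16.2% / 24.2% | 61.9 |
| 60 | 1,830 | 4.4% / 8.7% / 13.1% | 114.4 |

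For t = 30 to 60 min the range is 80 / 1,830 = 4.4% to 240 / 990 = 24.2%.

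**Step 4: the other gap in the row.** Read literally, the travel-time formula charges one round trip per family. It then omits 15 of 16 session trips in the standard arm (30t) and 1 of 2 in telerehab (2t). At t = 30 that is 900 against 60 min; at t = 60, 1,800 against 120 min. The net undercount of standard care, 28t, is 840 min at t = 30 and 420 min at t = 15. Both exceed the largest set-up total above, 240 min.

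On that literal reading, travel cancels between arms with equal travel times and only the 150 min remain. Adding set-up alone would then turn the sign at 9.4 min per session, so the two terms must be corrected together.

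**The case against.** **Not an exclusion, only an unwritten term.** Table 2 is introduced as model input, and the question sits under productivity loss. Neither place is exhaustive: session time is in the Productivity Loss list but has no row in Table 2, while time applying strategies has a Table 2 formula but is not among the numbered items. This stands as to intent; nothing shows a decision to leave set-up out. It does not remove the gap, because the one formula written for the row omits the input and the analyst is left to decide.

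**Undercounting confined to telerehab.** A reader might infer that caregiver time is undercounted in the telerehab arm only. The documents do not support that. The missing visit count in the same row hits the standard arm harder, although it is probably a drafting gap, given that transport cost is multiplied by trips. Control participants may also attend up to two sessions by video (Protocol Deviation and Per-protocol Analysis), so set-up time can arise there too.

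**Set-up as the sole added burden.** A reader might also take set-up to be the only extra parent time that video delivery brings. It is not: Visit 5b includes equipment orientation, and Annex 1 has a 30-min video preparation and observation block at baseline and a 30-min video observation at the end. None is in the formulas.

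**Size.** Comparing set-up only with the 150 min makes it look decisive. Against session and travel time together it is not. This objection stands in full.

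**Conclusion.** The point holds as a modest omission. As written, the societal cost leaves out a collected time cost of video sessions, and that omission leans towards telerehab. It amounts to 80 to 240 min per family at an assumed 5 to 15 min per session: enough to offset the in-session difference, but about 4% to 24% of the combined session and travel saving at an assumed 30 to 60 min of one-way travel. Break-even set-up is about 62 to 114 min per session in that travel range, and about 36 min even at 15 min of travel.

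It would be too strong to say that the omission could by itself decide the cost-saving verdict. That is unlikely, though these figures concern caregiver time only: the documents give no session charges or incomes from which to compute the full cost difference. They also assume full attendance and similar travel time and hourly income in the two arms. The direct medical cost perspective and the primary non-inferiority comparison are unaffected.

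**What to change.** Make one edit to Table 2 and to the list under Productivity Loss:

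1. Add a set-up term: video sessions attended × reported set-up time per session (in hours) × hourly income. Vary it in the planned one-way sensitivity analysis.
2. Multiply travel time by the observed number of clinic visits, matching the transport-cost formula.
3. Exempt set-up time from the rule under Data Cleaning Methodology and Approach that turns a reply of 0 into missing. If a share p of parents truly need no set-up time and the rest average m, the mean is (1 − p)m, but after recoding it becomes m, which overstates telerehab cost.
4. For control-arm video sessions, apply the telerehab-arm mean set-up time as a stated assumption, since the question is listed for telerehab parents only.

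It would also help to say whether the equipment orientation and the video observations are counted.

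The cost is a few lines of text and no new data collection. The set-up term makes the societal saving slightly smaller; the visit count works the other way relative to the literal formula.

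### The travel-time cost formula uses the survey-day journey for every parent, although the same row also collects the usual journey time from parents who say that day was not normal

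*Combined protocol and SAP*

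**What the plan says.** The Transport row under productivity loss in Table 2 lists three baseline questions in both arms. The first asks how long the journey to the unit took that day. The second is "Does it normally take you this long". The third is "If no, how long do you usually take". The formula beside them is "Time (in hour) required to travel to CDU today * 2 (two-way trip) * hourly income of parent surveyed".

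The Productivity Loss text lists the component as "time spent on travelling CDU for treatment (two-way trip", without saying whether that means the survey-day or the usual journey. The time horizon is the whole programme, about one year.

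Fares have a separate row, with a similar pair of questions on the mode and cost that day and the usual mode and cost. Its formula is "Transport Cost = Total no. of trips * Mean transport cost * 2". That formula carries a trip count and is not tied to the survey day. The Transportation Costs text likewise multiplies by the clinic visits actually observed.

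The data-cleaning table covers ranges, open-ended amounts, mixed text answers, missing entries and out-of-range values. It has no rule for choosing between the survey-day and usual journey times.

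**The concern.** The quantity wanted is travel time for treatment over about a year of visits. One day's journey is a proxy for it. The survey checks the proxy and, where the parent rejects it, collects a replacement. The formula has no branch for that answer, so an analyst who follows it literally keeps the rejected value. The baseline cost survey may also be completed by email or phone (Baseline Assessments, Visit 5a), in which case there may be no journey that day to report.

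What is at stake is one input to the societal cost comparison. The Cost-Effectiveness Analysis section rests its assessment on whether telerehab is cost-saving, and the arms differ mainly in the number of clinic sessions, so travel time is a relevant input. Nothing here touches the clinical outcomes.

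**Working it through.** **Plan's own figure.** The documents state no travel time, travel saving or hourly income, so there is no figure to reproduce. The check is in hours, with assumed inputs marked as such.

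**Inputs from the documents.** Table 1 of the cost-effectiveness section gives planned clinic sessions for the standard and telerehab arms: "Clinic-based intervention (45mins + 15mins) 16 sessions 2 sessions". The difference is 16 - 2 = 14 sessions, or 14 x 2 = 28 one-way legs.

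**Assumed inputs.** U = mean usual one-way time (0.5 to 1.0 h). f = share of parents whose survey-day journey was not normal (10% to 40%). d = net signed mean deviation among those parents (-0.25 to +0.5 h, with zero if deviations cancel).

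**Step 1: the formula as printed.** Hours per parent = 2 x survey-day time. With U = 0.75 h and no deviation this is 2 x 0.75 = 1.5 h in each arm, a difference of 0. With no visit count the formula yields no travel saving. Any survey-day error also cancels between randomised arms in expectation. The error reaches the arm comparison only once visits are applied.

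**Step 2: visits applied at the planned numbers.**
- Saving on usual time = 28 x U.
- Saving on survey-day time = 28 x (U + f x d).
- Error = 28 x f x d hours; relative error = f x d / U.

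Each minute of net mean discrepancy becomes 28 minutes (0.47 h) per child. For U = 0.75 h:

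| f | d (h) | Usual time (h) | Survey-day time (h) | Error |
|---|---|---|---|---|
| any | 0 | 21.0 | 21.0 | 0% |
| 10% | -0.25 | 21.0 | 20.3 | -3.3% |
| 20% | +0.25 | 21.0 | 22.4 | +6.7% |
| 20% | +0.5 | 21.0 | 23.8 | +13.3% |
| 40% | -0.25 | 21.0 | 18.2 | -13.3% |
| 40% | +0.5 | 21.0 | 26.6 | +26.7% |

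Over the full assumed grid the extremes are both at U = 0.5 h and f = 40%: 14.0 h becomes 11.2 h (-20%) at d = -0.25 h, or 19.6 h (+40%) at d = +0.5 h.

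**Step 3: deviations that average zero.** Take 66 per arm, usual time with mean 0.75 h and SD 0.25 h (assumed), and 20% of parents off by plus or minus 0.25 h with equal chance. The variance of one parent's value rises from 0.0625 to 0.0625 + 0.20 x 0.0625 = 0.075, so the standard error rises by a factor of sqrt(1.2) = 1.095. A simulation of 5,000 trials agrees: the mean saving is 21.0 h either way, and its standard error goes from 1.00 to 1.10 h. The cost is then about 10% in precision, with no bias.

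**The case against.** The strongest reply is that the survey-day word in the formula is shorthand. The usual-time question sits in the same row, in a table introduced as the model's input data, and other cells are equally informal. On that reading the analyst would use the usual time where it was given. This may be what is intended, and the documents do not show that the answer will be thrown away. But no text says it will be used, and the literal formula says otherwise, so the mismatch stands.

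A reader might go further and infer that the travel saving is mis-stated in a known direction. The documents do not support that. Bias needs systematically unusual survey days. The survey is given around a clinic visit at the same unit after several earlier visits, and nothing suggests that those journeys are atypical.

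A reader might also set the hours above against the planned 150-minute difference in therapy time (720 - 570). That is a different cost component; the relevant base is total travel saved.

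Nor do the documents show that the usual fare is ignored. The fare formula uses a mean cost not tied to the survey day, so there is only a silence about which answer enters it. Travel is also not the only route by which visit burden could enter: the employment rows of Table 2 ask about reduced hours and leave taken because of the intervention.

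Finally, this is one input to a cost analysis with one-way and probabilistic sensitivity analyses planned. That limits the consequence, although those analyses would not remove a systematic error in an input.

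**Conclusion.** The point holds as a minor inconsistency between a formula and the data collected for it. Followed as printed, the formula uses a journey time that some parents have said is unrepresentative, and the usual time enters no calculation. The effect is added noise in the societal travel cost, with bias only if survey-day and usual journeys differ systematically. Size and sign cannot be found from the documents. The -20% to +40% range rests on assumed journey times, shares and deviations, on full attendance at the planned sessions, and on a visit count that the printed formula lacks.

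That missing visit count is the larger fault in the same line. Correcting only the choice of journey time would still give no valid travel saving. The MSEL non-inferiority test is unaffected.

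**What to change.** Replace the travel-time formula in Table 2 with: usual one-way time x 2 x observed number of clinic visits x hourly income of the parent surveyed. Define usual one-way time as the survey-day answer if the parent says it is normal, and otherwise the usual-time answer. Use the same observed visit count as for transport cost.

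For consistency, state the matching rule for fares: that day's fare if the mode was the usual one, otherwise the fare for the usual mode.

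The cost is one line in Table 2 and, optionally, one for fares. All the answers needed are already in the baseline survey for both arms, and observed visits are already required for transport cost. Writing the rule down before the final analysis also removes a later discretionary choice over a cost input.
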